INDONESIA UNIVERSITY

THE EFFECT OF TETRAGONULA AFF TOLERANT PROPOLIS
ETHANOL EXTRACT. BUREAU OF ENDOMETRIOSIS LESI
GROWTH, APOPTOSIS ACTIVITY CHANGE AND NETWORK
ENDOMETRIOSIS ACTIVITIES

[figure not shown]
STUDY PROTOCOL

[name]

FACULTY OF MEDICINE
MEDICAL SCIENCE DOCTORAL PROGRAM

JAKARTA
AGUSTUS 2019

STUDY PLANNING

[figure not shown]
The study involved 80 endometriosis mice which were randomly divided into 16 distinct groups: the sham (SH) -0, SH-2, SH-4, SH-6, negative control (KN) -2, KN-4, KN groups -6, positive control (KP) -2, KP-4, KP-6, Dosage of Propolis 1 (P50) -2, P50-4, P50-6, Dosage Propolis 2 (P100) -2, P100-4, P100-6. All mice that will be made endometriosis models are certain to have a normal estrous cycle. The first laparotomy was performed to make an endometriosis model according to the Vivian technique, which was confirmed to be successful 30 days later with a second laparotomy. Subsequently given different treatment according to the study group and carried out a third laparotomy at the appropriate time (2, 4, and 6 weeks after the second laparotomy).

TREATMENT OF RAT

All rats were treated in the ARF IMERI FKUI laboratory. Standard care in research rate follows standard maintenance protocols according to Bauman¹³⁵ to provide optimal well-being for these rats, including: the need for social contact, a place to rest, a place to hide, exploration needs, the need for nutrition and free from environmental disturbances (e.g temperature, sound, etc.)

ESTRUS CYCLE EXAMINATION

The estrous cycle of rats was examined by taking vaginal lavage. Each rat in one cage was marked to distinguish the first to fifth mice. Vaginal discharge is taken by inserting the tip of a plastic pipette containing 10 μ L NaCl 0.9% into the rat's vagina, but not too deep. If the rat is considered aggressive, sampling can be carried out. The vaginal discharge is then placed on a glass slide. Glass slide that is used is different for each cage.

[figure not shown]

PROPOLIS ETANOL EXCRETION

Ethanol Propolis extract (EEP) is made from fine Propolis extracted with 96% ethanol using the method described in Pratami. EEP powder according to the treatment dose was dissolved in 10 cc of aqua before it was given to rat endometriosis models

1st LAPAROTOMY

[figure not shown]
1. Anaesthesia of rats (pentobarbital sodium, 50 mg / kg BW i.m.)
2. Perform Asepsis and antisepsis procedures in the abdomen of the rat

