2x QuantiTect SYBR Green PCR Master Mix	7,5 μ L
Primer forward	0,45 μ L
Primer reverse	0,45 μ L
Template cDNA	2 μ L
Total Volume	15 μ L

The reaction mix is then put into a 0.2 ml tube and homogenized by spin down for a few seconds then put into the Techne Prime Pro 48 [Techne] PCR machine and set according to the following table:

Real-time PCR cycle

Steps	Time	Temperature
PCR initial activation step	15 menit	95°C
Denaturasi	15 detik	95°C
Annealing	30 detik	57°C
Ekstensi	30 detik	72°C
Jumlah siklus	40	

The results are then compared with standard curves and analyzed

DATA ANALYSIS

Data on lesion area of endometriosis tissue models, Bax / Bcl-2, Caspase 3, IL-1B, and PGE2 ratios obtained from In Vivo research are numerical data that will be processed using SPSS 20. The data will be presented in the average form if normal distribution or median if not normally distributed. The normality of distribution will be known through the Shapiro Wilk Test. Differences in endometriosis responses between dose and duration groups were performed with the Anova test (normal distribution) or Kruskal Wallis (abnormal distribution). Changes in estrous cycles between groups are known through the chi square test.

To find out the binding of EEP active compounds, it was carried out using the in silico test. Compounds are said to bind when the value of ΔG is less than zero or negative. From the binding compounds, path analysis will be carried out to determine the relationship of the bonds with receptors related to the pathophysiology of endometriosis.

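### The planned comparison between duration groups cannot separate longer propolis treatment from natural lesion change, because no contrast against the time-matched negative control is specified

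*Combined protocol and SAP*

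**What the plan says.** All references are to the combined protocol and SAP.

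- **Study Planning, groups:** "The study involved 80 endometriosis mice which were randomly divided into 16 distinct groups". Five arms are listed. Sham has groups at 0, 2, 4 and 6 weeks. KN, the positive control (KP) and the two propolis doses (P50, P100) each have groups at 2, 4 and 6 weeks. The negative control is listed as "negative control (KN) -2, KN-4, KN groups -6".
- **Study Planning, timing:** the endometriosis model is "confirmed to be successful 30 days later with a second laparotomy". Treatment follows, and then a "third laparotomy at the appropriate time (2, 4, and 6 weeks after the second laparotomy").
- **Data Analysis:** "Differences in endometriosis responses between dose and duration groups were performed with the Anova test" if the distribution is normal, and Kruskal-Wallis if it is not. The section does not say whether the ANOVA is one-way or two-way. It names no dose-by-duration interaction and no contrast against KN, and it does not say how a duration difference will be interpreted.
- **2nd Laparotomy and Specimen Collection:** the steps at the second laparotomy include excising the lesion that has formed. The steps at the end of treatment include photographing the lesion for comparison with the starting lesion, and then collecting it.

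**The concern.** Every animal starts treatment at the same time after implantation, and each duration group is examined once, when its treatment ends. Animals treated for 6 weeks therefore also have lesions four weeks older than animals treated for 2 weeks, and are four weeks older themselves. If untreated lesions grow or regress over that period, P50-2, P50-4 and P50-6 will differ even if propolis does nothing. If natural growth and a true cumulative effect pull in opposite directions, they can cancel and the true effect is missed.

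Duration is one of the two factors on which the trial is built, with necropsies at three treatment times in every arm. The same issue affects lesion area and the protein outcomes, since all are measured at those times.

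**Working it through.** **1. Group count.** 4 sham + 3 KN + 3 KP + 3 P50 + 3 P100 = 16, which matches the plan. 80/16 = 5 per group if the split is equal. The group size is not stated, so 5 is an assumption.

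**2. Time since implantation at the endpoint.** 30 + 14 = 44, 30 + 28 = 58 and 30 + 42 = 72 days.

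**3. Can the two be separated?**
- Within one propolis arm, age = 30 + 7 × weeks. The correlation is 1, and the design matrix [1, age, weeks] has rank 2 of 3. They cannot be separated.
- With KN added, [1, arm, age, propolis weeks] has rank 4 of 4, and age correlates 0.35 with propolis weeks. They can be separated.

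**4. Rejection rate with inert propolis.** The documents give no SD, growth rate or alpha. Assumed: two-sided 5%, SD = 1, and untreated means 0, d/2 and d at weeks 2, 4 and 6. The F test on 2 df has noncentrality λ = n(d²/4 + 0 + d²/4) = nd²/2, with n animals per week. For d = 1, λ = 2.5 within one arm (n = 5) and 5.0 with both doses pooled (n = 10).

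| Drift d, week 2 to 6 | One arm, 12 error df | One arm, 48 error df | Both doses, 27 error df | Both doses, 48 error df |
|---|---|---|---|---|
| 0.5 SD | 9% | 10% | 14% | 15% |
| 1 SD | 22% | 26% | 46% | 48% |
| 1.5 SD | 45% | 53% | 82% | 84% |

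The 12 and 27 df are those of a one-way test on those animals alone. The 48 df come from a model on all 12 KN, KP, P50 and P100 groups (60 - 12).

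**5. KN-adjusted contrast.** C = (P100-6 - KN-6) - (P100-2 - KN-2). Drift common to both arms cancels, so the rejection rate with inert propolis stays at 5%.

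**6. What the unadjusted test responds to.** Simulation with 5 per group and 5,000 runs, using P50:

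| Scenario | ANOVA across P50 durations | KN-adjusted contrast |
|---|---|---|
| Ageing only, 0.5 SD per week | 71% | about 5% |
| Duration effect only, -0.5 SD per week | 70% | 60% |
| Both, equal and opposite | 5% | 59% |

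The unadjusted test responds to the sum of ageing and duration.

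**7. Cost in precision.**
- Within-arm change: SE = √(2/5) = 0.63 SD.
- KN-adjusted contrast: SE = √(4/5) = 0.89 SD.
- Ratio: √2 = 1.41.
- Power for a true 1 SD duration effect: about 34% for the within-arm change (if there is no ageing) and about 20% for the adjusted contrast.
- Detectable difference at 80% power (60 error df): 1.80 SD and 2.55 SD respectively.

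**The case against.** **The design is sound.** A reader might infer that treatment duration is hopelessly confounded with lesion age in this study. The documents do not support that. KN, KP and sham animals are randomised to the same weeks, so every propolis group has a concurrent control of the same lesion age. The confounding exists only within an arm. This stands, and it makes the point one about the analysis text and not about the design.

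**The test is not blind to duration.** A reader might also infer that the planned comparison measures ageing instead of duration. It responds to both: with a pure duration effect and no ageing it rejects 70% of the time in the simulation. This stands too. The fault is that the two cannot be told apart.

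**The sentence could mean a two-way ANOVA.** That reading is possible, and a factorial model would contain the needed term. But no interaction is written, the Kruskal-Wallis branch has none, and a duration main effect would still mix the two sources. Nor do the documents say that natural change will be reported as a treatment effect. They state no interpretation at all, so the defect is underspecification.

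**Each lesion is compared with its own starting picture.** This does not help. Change from day 30 still contains 2, 4 or 6 weeks of natural change, and the picture concerns the lesion itself, not the protein outcomes.

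**The percentages are hypothetical.** This is correct. They rest on an assumed drift, an assumed 5 per group and a choice of error df.

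**Conclusion.** The point holds as one of specification. As written, a difference between the 2-, 4- and 6-week groups cannot be attributed to longer propolis treatment. The groups that would allow attribution are already in the study, but the plan does not say they will be used for this.

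The size depends on how much untreated lesions change, which the documents do not give. For drifts of 0.5 to 1.5 SD, the false-positive rate runs from 9% to 53% within one arm and from 14% to 84% with both doses pooled. A true effect can also be masked.

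Three assumptions remain:
- 5 animals per group.
- KN is the untreated or vehicle arm. The document does not say which arm receives the water, so this is inferred.
- The lesion stays in place after day 30. The excision step at the second laparotomy and the endpoint comparison with the starting lesion do not fit together as written. If the whole lesion were removed, the ages of 44, 58 and 72 days would not apply, although time since surgery and animal age would still move in step with duration.

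**What to change.** In Data Analysis:

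1. Specify a two-way ANOVA (arm by week) on the KN, KP, P50 and P100 groups at weeks 2, 4 and 6. Base any duration claim on the arm-by-week interaction against KN, for example (P100 - KN at week 6) minus (P100 - KN at week 2), and the same for P50.
2. If normality fails, test the same contrast on transformed or rank-aligned data, or by a permutation test, in place of Kruskal-Wallis across durations. Name the method in advance.
3. State that within-arm differences between weeks, and the week main effect, are descriptive and are not read as an effect of treatment duration.

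Separately, reconcile the excision step under 2nd Laparotomy with the endpoint comparison under Specimen Collection, and state what KN receives.

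The cost is wording only, with no new animals or measurements. The downside is precision: the standard error is 0.89 SD against 0.63 SD, and power for a 1 SD duration effect is about 20% against 34%. Pooling the two doses against KN would reduce the standard error to √(2/10 + 2/5) = 0.77 SD (detectable difference 2.21 SD). The report should say that a non-significant interaction at this sample size is weak evidence against a duration effect.

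### The named rank test takes one grouping factor, but the design randomises two (arm and duration); no way of applying it gives a sound test of dose or duration, and a stratified rank test would

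*Combined protocol and SAP*

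**What the plan says.** STUDY PLANNING sets the layout: "The study involved 80 endometriosis mice which were randomly divided into 16 distinct groups". Sham has groups at 0, 2, 4 and 6 weeks. The negative control (KN), positive control (KP) and two propolis doses each have groups at 2, 4 and 6 weeks; for propolis these are "Dosage of Propolis 1 (P50) -2, P50-4, P50-6, Dosage Propolis 2 (P100) -2, P100-4, P100-6". The animals "carried out a third laparotomy at the appropriate time (2, 4, and 6 weeks after the second laparotomy", so each duration is observed in different animals. Arm and duration are therefore both between-animal, randomised factors.

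DATA ANALYSIS lists the outcomes ("Data on lesion area of endometriosis tissue models, Bax / Bcl-2, Caspase 3, IL-1B, and PGE2 ratios obtained from In Vivo research are numerical data"), gives the rule for choosing a test ("The normality of distribution will be known through the Shapiro Wilk Test") and then the comparison: "Differences in endometriosis responses between dose and duration groups were performed with the Anova test (normal distribution) or Kruskal Wallis (abnormal distribution". It does not say whether the groups compared are the cells, the arms with durations combined, the durations with arms combined, or the arms within each week. It names no two-factor model, stratified rank test or follow-up comparison. It gives no significance level, SD, effect size or power.

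**The concern.** A one-factor rank test on a two-factor design has to do something with the second factor, and each option has a cost.

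- **Durations pooled to compare arms.** Animals from weeks 2, 4 and 6 are ranked together. Any duration effect widens the spread of ranks that the test treats as noise. Because durations are balanced over arms, it does not move the arm rank sums by a matching amount, so the statistic is too small. The test is calibrated only if duration has no effect and is otherwise conservative. The duration test with arms pooled suffers in the same way, and there an effective positive control counts as noise.
- **All cells compared.** A significant result may come from dose, duration or both.
- **Arms compared within each week.** Duration noise disappears, but each test rests on about 5 animals per arm.

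Dose and duration are the two things the layout was built to study. The risk is that a real propolis or duration effect is reported as absent, or that an overall rejection is credited to dose without support.

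**Working it through.** **Layout.** 4 sham groups + 4 arms × 3 durations = 16 groups, and 80 / 16 = 5 animals per group if allocation is equal. ESTRUS CYCLE EXAMINATION is consistent with this: "Each rat in one cage was marked to distinguish the first to fifth mice". The plan has no power figure to reproduce.

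**Assumed inputs.** 4 arms (KN, KP, P50, P100) × 3 durations × 5 animals = 60; within-cell SD 1; two-sided 5%; additive arm effects of 0, -1, -0.5 and -1 SD; a shift of T SD per two-week step, with T = 0, 0.5, 1 and 1.5.

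**Statistics.**
- Pooled Kruskal-Wallis: H = 12/[N(N+1)] × Σ R²/15 − 3(N+1), with N = 60 and R the arm rank sums; chi-squared, 3 df.
- Stratified by week: rank 1 to 20 within each week and let S be an arm's sum of three weekly mean ranks. The null mean of S is 3 × 21/2 = 31.5, and the statistic is Σ(S − 31.5)² × 12×5/(20×3×21) = Σ(S − 31.5)²/21; chi-squared, 3 df.
- All cells: Kruskal-Wallis on 12 groups; chi-squared, 11 df.
- Single week: Kruskal-Wallis on 4 arms × 5 animals.

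**Simulation (20,000 runs per setting), power for the arm effect:**

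| Step T (SD) | Pooled | Stratified by week | Single week |
|---|---|---|---|
| 0 | 71% | 69% | 20% |
| 0.5 | 62% | 69% | 20% |
| 1 | 35% | 69% | 20% |
| 1.5 | 9% | 69% | 20% |

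**Rejection rate with no arm effect:**

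| Step T (SD) | Pooled | Stratified by week | 12 cells |
|---|---|---|---|
| 0 | 4.5% | 4.4% | 3% |
| 0.5 | 2.4% | 4.6% | 35% |
| 1 | 0.4% | 4.9% | 98% |
| 1.5 | 0.0% | 4.7% | 100% |

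**Hand check on the ANOVA analogue.** The arm effects have mean -0.625 and squared deviations 0.3906 + 0.1406 + 0.0156 + 0.1406 = 0.6875, so the noncentrality is 15 × 0.6875 = 10.31. Leaving duration out adds 60 × (2/3)T² = 40T² to the residual sum of squares on 56 df. The residual mean square becomes 1 + 40T²/56 = 1.00, 1.18, 1.71 and 2.61. The critical F(3, 56) of 2.77 then acts like 2.77, 3.26, 4.75 and 7.22 against the true error. Treating that inflation as fixed, power is about 74%, 66%, 41% and 15%, and the null rejection rate is about 5.0%, 2.8%, 0.5% and under 0.1%. Simulated power for the one-way ANOVA agrees (74%, 65%, 40%, 13%); the two-way model stays at 73-74%.

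**Duration test.** With a true step of 0.4 SD and the arm pattern multiplied by 0, 1, 2 and 3, pooled Kruskal-Wallis has 56%, 48%, 25% and 7% power, against 53-54% stratified by arm.

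**Other settings.** Log-normal data with effects additive on the log scale give the same rank-test results (pooled 71%, 61%, 34% and 9%; stratified 69-70%), as they must, because ranks do not change under a monotone transformation. Five arms including sham at 2, 4 and 6 weeks give 73%, 64%, 33% and 7% pooled, against 72% stratified.

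**The case against.** The strongest reply is that the plan never says it pools anything. That stands: pooling is one reading of an unspecified sentence, and the groups could equally be the cells or the arms within each week. A reader might infer that the plan commits to pooled tests; the text does not support that. But the other readings do not rescue the rank test, since one cannot attribute a rejection and the other has about 20% power.

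A reader might also infer that the ANOVA is one-way. The documents do not say so; an ANOVA on dose and duration may already mean a two-factor model. For that branch the point is only that the model should be stated.

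A third tempting reading is that the pooled arm test has a joint null of no dose and no duration effect, so that duration alone could produce a false dose finding. That is wrong. With equal numbers per week in each arm, the arm distributions are equal whenever arm has no effect, and the pooled test rejects less often, not more, as duration grows. The joint null belongs to the all-cells test.

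Two further limits stand. Kruskal-Wallis is reserved for non-normal data, and most figures here use normal errors; the log-normal results answer that for the rank tests. The loss is also modest at a 0.5 SD step (about 7 points) and becomes severe only from about 1 SD, which is 2 SD between weeks 2 and 6.

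**Conclusion.** The point holds as a conditional one, but it is more than missing detail: every way of running the named one-factor rank test on this layout is either weaker or unable to isolate dose from duration, and a better test using the factors already randomised is available. Under the assumptions stated, pooling costs nothing if duration has no effect, about 7 points of power at a 0.5 SD step, about 34 at 1 SD and about 60 at 1.5 SD. The direction follows from the design; the sizes depend on an assumed SD, effect pattern, additivity and 5 animals per cell, none of which the documents give. Whether an interaction should be tested is a separate question.

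**What to change.** In DATA ANALYSIS:

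1. State that the ANOVA is a two-way model with arm and duration, and that the dose and duration tests both come from it.
2. Replace Kruskal-Wallis with a stratified rank test. For arms, rank within each week and combine the weeks; for duration, rank within each arm and combine the arms. Take p-values by permuting animals within stratum only. In this balanced layout the chi-squared reference was also close to nominal for the arm test (4.4% to 4.9%).
3. Apply both to the arms present at 2, 4 and 6 weeks. The week-0 sham group has no counterpart in the other arms and should be described separately.

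This takes a few sentences and a little more analysis work, with no extra animals or measurements. If the other factor truly has no effect, the rank test loses about 2 points of power (71% to 69% for arms, 56% to 54% for duration) and the ANOVA less than 1 (74.4% to 73.9%).

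### The estrous comparison relies on a large-sample chi-square with about five rats per group and names no exact test or treatment contrast

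*Combined protocol and SAP*

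**What the plan says.** Study Planning: "The study involved 80 endometriosis mice which were randomly divided into 16 distinct groups". The groups are arms crossed with duration: sham (SH) at 0, 2, 4 and 6 weeks, and negative control (KN), positive control (KP), propolis 50 (P50) and propolis 100 (P100) at 2, 4 and 6 weeks each. On entry, "All mice that will be made endometriosis models are certain to have a normal estrous cycle".

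Estrus Cycle Examination: "Each rat in one cage was marked to distinguish the first to fifth mice". This fits five animals per group but does not state it.

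Data Analysis: "Changes in estrous cycles between groups are known through the chi square test". Nothing further is given for this endpoint. The readable text does not say which groups are compared, what categories a change falls into, when it is judged, what significance level applies, or what is done when counts are small. The sentence before it, on the numerical endpoints, is more specific: "Differences in endometriosis responses between dose and duration groups were performed with the Anova test". That section also gives a fallback for non-normal numerical data. The chi-square has no fallback.

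**The concern.** The chi-square p-value is a large-sample approximation, and the design gives very small groups. If the approximation is poor, a result near 5% could be declared significant or dismissed wrongly. Separately, one overall test across many arm-by-duration groups asks only whether any group differs. A significant result would not show whether propolis or dienogest is responsible. A non-significant one could hide an effect common to all three durations. The estrous endpoint is a planned comparison, so the analysis should be able to say something about treatment.

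**Working it through.** **Inputs from the documents.** 80 animals and 16 groups; the listed groups count 4 + 3 + 3 + 3 + 3 = 16. There is no power or sample-size figure to reproduce.

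**Assumptions.** Equal split, 80/16 = 5. Yes/no outcome (cycle abnormal or not). Nominal level 5%. The documents give no abnormality rates, so a range is used.

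**Expected counts.** With n animals per group and overall rate p, the cells are n·p and n·(1−p).
- 16 groups, or five arms within one week (n = 5): 5p and 5(1−p), both below 5 for any p strictly between 0 and 1. At 20% they are 1.0 and 4.0; at 50%, 2.5 and 2.5.
- Arms pooled over weeks (n = 15; 20 for SH if SH-0 is included): at 20%, 3.0 and 12.0 (SH 4.0 and 16.0); at 50%, 7.5 (SH 10). With n = 15 the abnormal cells are still below 5 when p is under 1/3, since 15p < 5.

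**Degrees of freedom.** (groups − 1) × (categories − 1): 15 for 16 groups and two categories; 4 for five arms, within a week or pooled. More categories would raise these.

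**One table worked through.** Two abnormal rats, both in one of the 16 groups.
- p = 2/80 = 0.025, so the expected abnormal count per group is 0.125.
- Sum of squared deviations = (2 − 0.125)² + 15 × 0.125² = 3.516 + 0.234 = 3.75.
- Chi-square = 3.75 / (5 × 0.025 × 0.975) = 3.75 / 0.1219 = 30.8 on 15 df, p = 0.009.
- Exact: once the first abnormal rat is placed, 4 of the other 79 animals share its group. The chance that both fall together is 4/79 = 0.051.

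The approximation understates this p-value more than fivefold and moves it across 5%.

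**Average size.** Simulating the 16-group test with a common rate of 5% to 50% gives true size of about 2.6% to 4.2%. For five arms within one week it falls to 0.5% at a 5% rate.

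**Power by simulation.** The comparison is Pearson chi-square on the 15 treated arm-by-duration groups (SH-0 left out) against Pearson chi-square on five arms of 15. Assumed rates are in the order SH/KN/KP/P50/P100.

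| Assumed abnormal rates | 15 groups | Five arms |
|---|---|---|
| 10/10/40/30/40%, constant over weeks | 26% | 55% |
| 10/10/50/40/50%, constant | 48% | 83% |
| 10/10/70/50/70%, constant | 91% | 99% |
| 10/10/80/60/80% at week 6 only, otherwise 10% | 95% | 25% |
| Growing over weeks 2/4/6: KP and P100 10/40/80%, P50 10/30/60%, others 10% | 91% | 62% |

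Replacing the pooled Pearson test with an exact permutation test of arms stratified by week gives about 55% and 81% in the first two rows, so that gain does not depend on the approximation.

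**Pairwise contrasts.** Power of Fisher's exact test, 15 v 15, two-sided 5%, is the sum over i and j of Bin(i; 15, 0.10) × Bin(j; 15, q) where the Fisher p-value is at most 0.05. It is 15% for q = 30%, 32% for q = 40% and 54% for q = 50%, before any multiplicity adjustment.

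**The case against.** The strongest reply is that the plan never says the 16 groups are compared. The dose-and-duration wording belongs to the sentence on numerical endpoints. If arms are pooled over weeks, the test has 4 df and not every expected count is below 5. This stands: the small-count statement holds for two readings of the sentence and not for the third. The yes/no outcome is also inferred, because a normal cycle at entry does not fix the categories at follow-up.

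A reader might infer that the planned test costs about half the power. The documents do not support that as a general figure. They give no rates. The loss is about half for moderate effects constant over weeks, small for large ones (91% against 99%), and reversed when the effect depends on duration, which this design varies deliberately. Replacing the arm-by-duration comparison with a pooled arm test would therefore be a trade-off, not a correction.

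A reader might also infer inflated false positives. The simulated size is below 5% throughout, and an expected count of 5 is a rule of thumb. What survives is narrower: individual p-values can be badly wrong even though average size is only mildly conservative.

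Finally, the remedy is not powerful. At 15 v 15 the pairwise contrasts detect moderate effects about a third to half of the time, and less after adjustment. That is a limit of the sample size and is not a reason to keep the approximation.

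**Conclusion.** The point holds in a limited form. The estrous analysis names only a large-sample chi-square and leaves both the groups and the categories undefined. Given five animals per group and a yes/no outcome, every expected count is below 5 if the 16 groups, or the arms within a week, are compared. Single-table p-values can then mislead (0.009 against 0.051), while average size for the 16-group test is about 2.6% to 4.2%. An overall test across up to 16 groups also does not identify which treatment acts. Its power relative to an arm-level test can go either way, and the figures rest on assumed rates. This is a cheap improvement that should be made; it does not invalidate the study.

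**What to change.** Amend the Data Analysis section as follows.

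- Define the estrous outcome (its categories and when it is judged) and the groups compared.
- Replace the chi-square with an exact test: Fisher-Freeman-Halton or a permutation test.
- Add an arm comparison stratified by duration (weeks 2, 4 and 6), with exact contrasts of KP, P50 and P100 against KN under a stated multiplicity adjustment such as Holm. Leave SH-0 out of these comparisons, as it has no treatment period.
- Keep the arm-by-duration comparison as a separate exact test, and say in advance which of the two overall tests is the main one.

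The cost is a few sentences and a little more analysis on the same animals and data. The team should confirm that SPSS 20 as installed can run the exact tests, or name other software. Exact tests are slightly more conservative, and the contrasts at 15 v 15 keep limited power, so a non-significant result should be reported with confidence intervals and not read as no effect.

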Protein samples were obtained from endometriosis tissue taken by the treatment group. The lysis network uses a lysis buffer solution at 4 ° C for 30 minutes. The total protein is then broken down based on its molecular weight by the SDS-PAGE (Sodium Docecyl Sulphate-Polycramide Gel Electrophoresis) method and transferred to the PVDF (Polyvinylidene Difluoride) membrane. The membrane is then incubated with primary antibodies (Anti-Bax antibody [Abcam], Anti-Bcl-2 antibody [Abcam], Anti-Cleaved Caspase-3 antibody [Abcam], Anti-IL-1B antibody [Abcam]), followed by incubation with secondary antibodies (Horse-Radish Peroxidase [Santa Cruz Biotechnology]). Proteins that have been bound to antibodies are then viewed using enhanced chemiluminescent reagent kits [Boster Bio]

Molecular docking

Twenty-three compounds contained in Propolis were tested by screening using rule 5 (Lipinski's rule) consisting of: molecular weight <500 Dalton, <10 hydrogen donor bonds, <10 hydrogen acceptor bonds, partition coefficient values between -5 to 5. The screening results determine which compounds can enter the body and can work in endometriosis tissue. Furthermore, the three-dimensional shape is made of compounds which have passed the first stage. This process was created using the Marvin Sketch program. Furthermore, the compound that has been formed is stored as a ligand with extension pdb (protein data bank). Look for NFκB receptor proteins, estrogen A, estrogen B, progesterone A and progesterone B in the protein data bank, which will be stored as protein. Ligands and proteins are tested using standard Lamarckian algorithms in the Autodock program. The results obtained are in the form of bond energy (ΔG), where smaller results indicate a higher likelihood of interaction.

Examination of PGE2 receptor mRNA expression

Isolation of RNA in Endometriosis Tissue Samples

The RNA isolation process is carried out by first preparing a mixture consisting of 400 μL RB Buffer and 4 μL Beta-Mercaptoethanol. Then, the tissue is removed and placed in a later RNA, then the later RNA is removed and mixed with RB buffer and beta mercaptoethanol

RNA spectrophotometry

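### The docking rule counts any negative ΔG as binding, with no minimum affinity and no reference ligand, so very weak scores can enter the path analysis

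*Combined protocol and SAP*

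**What the plan says.** The in silico paragraph of DATA ANALYSIS names docking as the means of establishing binding ("To find out the binding of EEP active compounds, it was carried out using the in silico test") and then gives the criterion: "Compounds are said to bind when the value of ΔG is less than zero or negative". The call has a consequence: "From the binding compounds, path analysis will be carried out to determine the relationship of the bonds with receptors".

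The Molecular docking section describes what comes before. "Twenty-three compounds contained in Propolis were tested by screening" against Lipinski's rule, which covers molecular weight, hydrogen bonds and partition coefficient. Those that pass are modelled ("the three-dimensional shape is made of compounds which have passed the first stage") and docked: "Ligands and proteins are tested using standard Lamarckian algorithms in the Autodock program". The targets are NFκB and "estrogen A, estrogen B, progesterone A and progesterone B in the protein data bank", five in all. The output is described as graded: "The results obtained are in the form of bond energy (ΔG), where smaller results indicate a higher likelihood of interaction".

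No section states a minimum affinity, a unit for ΔG, or a reference ligand docked for comparison. Dienogest appears only as an animal treatment, under THE TREATMENT.

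**The concern.** A cut-off at zero separates negative scores from positive ones, and the plan attaches the word binding to that split. A score just below zero and a strongly negative score receive the same label and the same entry to the path analysis. Without a reference ligand docked under the same settings, a reader cannot tell whether a given ΔG is good or poor for that receptor.

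At stake is the mechanistic claim. Links from propolis compounds to the NFκB, oestrogen and progesterone receptors could be drawn where the predicted affinity is negligible.

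**Working it through.** The plan gives no docking score or threshold calculation, so there is no figure of its own to reproduce. The check has two parts: what a score near zero means, and how many weak scores the rule might admit.

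**Inputs from the documents**
- Cut-off: ΔG < 0 (DATA ANALYSIS).
- Compounds: 23 before the Lipinski screen (Molecular docking). The number passing is not given, so 23 is an upper limit.
- Receptors: 5 (Molecular docking). With one structure each, at most 23 × 5 = 115 compound-receptor pairs.

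**Assumptions (not in the documents)**
- ΔG is a standard binding free energy in kcal/mol with a 1 mol/L reference state.
- R = 1.987 × 10⁻³ kcal/mol/K and T = 298.15 K, so RT = 0.5924 kcal/mol.
- For the counts, scores at a receptor are normal with the stated mean and SD.

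**Step 1: what the cut-off admits.** Kd = exp(ΔG/RT).
- ΔG = 0: exp(0) = 1 mol/L. This does not depend on the energy unit or the temperature.
- ΔG = -1: exp(-1.688) = 0.185 mol/L.
- ΔG = -2: exp(-3.376) = 0.0342 mol/L, or 34 mmol/L.
- ΔG = -4: exp(-6.752) = 0.00117 mol/L, or about 1.2 mmol/L (about 1.5 mmol/L at 310 K).

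For scale, a Kd of 10 µmol/L needs about -6.8 kcal/mol and 1 µmol/L about -8.2. The rule treats molar, millimolar and micromolar predictions alike.

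**Step 2: how many weak scores might be admitted.** Take -4 kcal/mol as an illustrative marker for weak. Expected number weaker than -4 per receptor = 23 × P(score > -4).
- Mean -8, SD 1: 23 × P(Z > 4) = 23 × 0.00003 = 0.0007, practically none.
- Mean -8, SD 2: 23 × P(Z > 2) = 23 × 0.0228 = 0.52.
- Mean -5, SD 2: 23 × P(Z > 0.5) = 23 × 0.3085 = 7.10.

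The zero rule removes almost none of these. In the last case it rejects 23 × P(Z > 2.5) = 23 × 0.0062 = 0.14, so about 7.10 - 0.14 = 6.96 weak scores are still called binders. In the second case the number rejected is 23 × P(Z > 4) = 0.0007.

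**Step 3: whether the rest of the text limits the rule.** The Lipinski screen filters before docking, but none of its criteria is affinity. The statement that a smaller ΔG means a likelier interaction gives an order and no threshold. Neither restricts which negative scores count.

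**The case against.** The strongest reply is that no harm is shown. The documents contain no scores, and the unit, means and SDs above are all assumed. If the scores cluster near -8, the zero rule admits hardly any weak ones. This stands: the wording lets very weak scores qualify, but whether any compound scores that weakly is unknown. A reader might infer that the path analysis will be filled with negligible links; the documents do not support that.

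A second reply is that the sign test may be only a permissive screen, with strength interpreted afterwards on the graded scale in Molecular docking. That is compatible with the text, which does not say that strength is discarded. But it states no later step that uses strength, and binding is defined by sign alone.

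A reader might also infer from the per-compound wording that it is open whether a compound must score negative at one receptor or at all five. The text does not invite an all-five rule. Ligands are docked against listed proteins and the path analysis concerns bonds with receptors, so the natural reading is pair by pair. That ambiguity is not part of this point.

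Finally, a reference plus a margin is itself a discretionary cut-off, and pre-specification is moot if docking is finished; the tenses in the two sections are mixed. Both remarks are fair. They are reasons to make ranked reporting beside a reference the core of the remedy and to label any late threshold as post hoc.

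**Conclusion.** The concern holds in a limited form. The plan states a complete binding rule, ΔG below zero, that decides which docked compounds reach the path analysis, and nothing else in the documents sets a floor on affinity or provides a comparator.

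That weak scores qualify follows from the wording. Expressing this as a Kd rests on the assumed free-energy reading, and the values for non-zero scores also rest on the assumed unit and temperature. The number of weak scores admitted cannot be determined: the scenarios run from practically none to about 7 of 23 per receptor, and they also rest on normality and on all 23 compounds passing the Lipinski screen.

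A reader might take this as a weakness in the trial's main results. It is not. Lesion area, Bax/Bcl-2, caspase 3, IL-1B, PGE2 and the estrous cycle are compared without reference to the docking. The point is a cheap improvement that should be made so that the in silico mechanism claims can be interpreted.

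**What to change.** Replace the sign rule in DATA ANALYSIS with a comparison for each compound-receptor pair:

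- For each receptor, dock a named reference ligand with the same settings: the ligand in the downloaded structure or, if there is none, a named known ligand.
- Report all ΔG values, with their unit, ranked beside the reference. Do not describe a compound as binding because its score is negative.
- Call a pair a likely binder, and draw its link in the path analysis, only if its ΔG is at or below the reference ΔG, or within a margin stated with its unit and reason before the scores are examined.
- If a receptor has no reference, rank its scores and make no binding call.
- If docking is already done, add the reference runs and label any threshold post hoc.

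If scores are in kcal/mol, a margin can be justified as a fold change in Kd, exp(margin/RT) at 298 K: 1 is 5.4-fold, 1.36 is tenfold and 2 is 29-fold.

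The cost is about five extra docking runs (one per receptor) in software already in use, plus the work of choosing and justifying the reference ligands and any margin. Fewer compounds will be called binders, and the margin drives how many. In an assumed example with mean -6, SD 1.5 and reference -9 kcal/mol, a margin of 0 passes 23 × P(Z ≤ -2) = 23 × 0.0228 = 0.5 compounds per receptor, and a margin of 2 passes 23 × P(Z ≤ -0.667) = 23 × 0.2525 = 5.8. The full ranked list therefore has to be reported whatever margin is chosen.
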